- 5) Collected prior to C1D1 treatment; at the end of 2 cycles, and to document progression or CR at any time point.
- 6) The diary must begin the day the patient starts taking the medication and must be completed per protocol and returned to the treating institution.
- 7) Affected immunoglobulin refers to the baseline M-protein type, that is, IgG, IgA, IgD, or IgM. Not applicable if patient “non-secretory” or if patient has no heavy chain, i.e. light chain myeloma.
- 8) Collected prior to C1D1 and C1D22; then every cycle prior to D1 treatment; and to document progression or CR at any timepoint.
- 9) The following testing may be done if clinically indicated: Myeloma FISH, plasma cell proliferation, and flow cytometry (MRD)
- 10) Does not need to be repeated at Cycle 1 Day 1. Baseline values can be used for Cycle 1.
- 11) If patient is stable after 2 cycles, physical exam can be decreased to Weeks 1 and 7 of each cycle.
- 12) Only if clinically indicated for MRD negative patients every 12 weeks.
- 13) Urine Electrophoresis required only if used to assess disease response.

R) Research funded (see Section 19.0). Will be charged to study and not to patient's account.

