## 7.0 Protocol Treatment

### 7.1 Treatment Schedule

Cycle length: 84 days.

Agent	Route	Dose	Day	Retreatment
Ixazomib	PO	4 mg	1, 8, 15, 29, 36, 43, 57, 64, 71	Every 84 days
Pembrolizumab	IV	200mg	Day 1, 22, 43, 64	Every 84 days
Dexamethasone	PO	40 mg	1, 8, 15, 29, 36, 43 57, 64, 71	Every 84 days

7.2 For this protocol, the patient must return to the consenting institution (Mayo Clinic) for evaluation at least every 21 days ( $\pm$  1 day). Treatment by a local medical doctor (LMD) is not allowed. Note: If patient is stable after 2 cycles, physical exam can be reduced to Weeks 1 and 7 of each cycle.

7.3 Patients are allowed to collect stem cells after 1 cycle of initial therapy. Stem cells can be collected using standard institutional protocols. Any delay beyond 4 weeks should be discussed with the study PI prior to reinitiating protocol therapy.

7.4 Patients should be instructed to swallow ixazomib capsules whole, with water, and not to break, chew, or open the capsules. The ixazomib should be taken on an empty stomach (no food or drink apart from 240 mL of water), at least 1 hour before or no sooner than 2 hours after food. Each capsule should be swallowed separately with a sip of water. A total of approximately 240 mL (about 1 cup/8 oz) of water should be taken with the capsules.

Missed doses can be taken as soon as the patient remembers as long as the next scheduled dose is 72 hours or more away. Patients who vomit a dose after ingestion will not receive an additional dose, but should resume dosing at the time of the next scheduled dose.

Drug will be administered only to eligible patients under the supervision of the investigator or identified sub-investigator(s). The drug will be prepared under the supervision of a pharmacist, or appropriately qualified and trained personnel.

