7.5 Dexamethasone (Cycles 1-4, maximum of 1 year)

- Dexamethasone may be self-administered by the subject on an outpatient basis.
- Missed doses of dexamethasone will not be made up. Procedures for dose reductions and delays are summarized in Section 8.0.
- Dexamethasone is commercially available. Accurate records will be kept in the source documents of all drug administration (including dispensing and dosing).

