## Appendix II PATIENT MEDICATION DIARY

Name \_\_\_\_\_ Study ID \_\_\_\_\_

Please complete this diary on a daily basis. Write in the amount of the dose of Ixazomib and dexamethasone that you took in the appropriate "Day" box.

On the days that you do not take any study drug, please write in "0". If you forget to take your daily dose, please write in "0", but remember to take your prescribed dose at the next regularly scheduled time.

Please drink at least 6 to 8 cups of liquid per day to help drug absorption. Swallow pills whole, with water, and do not to break, chew, crush or open the pills. The study drugs should be taken on an empty stomach (no food or drink) at least 1 hour before or at least 2 hours after a meal. Each pill should be swallowed separately with a sip of water. A total of approximately 8 ounces (240 mL) of water should be taken with the pills.

If you experience any health/medical complaints or take any medication other than ixazomib or dexamethasone, please record this information.

Week of:

Study Drug	Day 1	Day 2	Day 3	Day 4	Day 5	Day 6	Day 7
Ixazomib							
Dexamethasone							

Week of:

Study Drug	Day 8	Day 9	Day 10	Day 11	Day 12	Day 13	Day 14
Ixazomib							
Dexamethasone							

Week of:

Study Drug	Day 15	Day 16	Day 17	Day 18	Day 19	Day 20	Day 21
Ixazomib							
Dexamethasone							

Week of:

Study Drug	Day 22	Day 23	Day 24	Day 25	Day 26	Day 27	Day 28
Ixazomib							
Dexamethasone							

Week of:

Study Drug	Day 29	Day 30	Day 31	Day 32	Day 33	Day 34	Day 35
Ixazomib							
Dexamethasone							

Week of:

Study Drug	Day 36	Day 37	Day 38	Day 39	Day 40	Day 41	Day 42
Ixazomib							
Dexamethasone							

Week of:

Study Drug	Day 43	Day 44	Day 45	Day 46	Day 47	Day 48	Day 49
Ixazomib							
Dexamethasone							

Week of:

Study Drug	Day 50	Day 51	Day 52	Day 53	Day 53	Day 55	Day 56
Ixazomib							
Dexamethasone							

Week of:

Study Drug	Day 57	Day 58	Day 59	Day 60	Day 61	Day 62	Day 63
Ixazomib							
Dexamethasone							

Week of:

Study Drug	Day 64	Day 65	Day 66	Day 67	Day 68	Day 69	Day 70
Ixazomib							
Dexamethasone							

Week of:

Study Drug	Day 71	Day 72	Day 72	Day 74	Day 74	Day 76	Day 77
Ixazomib							
Dexamethasone							

Week of:

Study Drug	Day 78	Day 79	Day 80	Day 81	Day 82	Day 83	Day 84
Ixazomib							
Dexamethasone							

My next scheduled visit is:

If you have any questions, please call:

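### Section 7.4 allows a missed ixazomib dose to be taken late, but the patient diary tells patients to record a zero and wait for the next scheduled dose

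*Combined protocol and SAP*

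**What the plan says.** Section 7.4 tells patients how to take ixazomib capsules and then deals with forgotten doses: "Missed doses can be taken as soon as the patient remembers as long as the next scheduled dose is 72 hours or more away". The sentence does not name the drug, but it stands in the ixazomib instructions, and dexamethasone has its own rule in Section 7.5: "Missed doses of dexamethasone will not be made up".

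The diary in Appendix II covers both self-administered drugs together: "Write in the amount of the dose of Ixazomib and dexamethasone that you took". Its missed-dose text begins "If you forget to take your daily dose, please write in" and asks for a zero. The patient is then told to "remember to take your prescribed dose at the next regularly scheduled time". The 72-hour allowance is not mentioned and the two drugs are not separated.

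The diary is a required study document. A footnote to the schedule in Section 4.1 says that it "must be completed per protocol and returned to the treating institution".

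**The concern.** Two operative texts answer the same practical question differently: what does a patient do after forgetting an ixazomib capsule? Under 7.4 the patient may still take it, within a limit. Under the diary the patient leaves it and waits.

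Both drugs are taken on the same nine days of an 84-day cycle, so the next scheduled time is 7 or 14 days after the missed day. A patient who follows the diary therefore loses a dose that the protocol would have allowed. Two patients who forget and remember at the same times can receive different amounts of ixazomib, depending on which text they were guided by.

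The record would not show why. The diary asks for a zero both on days without study drug and for a forgotten dose. A zero on a dosing day with no later entry does not show whether the patient remembered too late for 7.4 to apply, or remembered in time and waited as the diary directs.

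**Working it through.** The plan gives no figure on this point, so the check is a comparison of texts plus arithmetic on the dosing calendar.

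**Inputs**
- Ixazomib days, from the table in Section 7.1: "1, 8, 15, 29, 36, 43, 57, 64, 71", repeated every 84 days, so Day 1 of the next cycle is Day 85.
- Starting dose, same table: 4 mg.
- Limit in Section 7.4: the next scheduled dose must be at least 72 hours away.

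**Rules side by side**

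| Drug | Protocol text | Diary | Agree? |
|---|---|---|---|
| Dexamethasone | 7.5: a missed dose is not made up | Enter zero, wait for next scheduled time | Yes |
| Ixazomib | 7.4: a late dose is allowed if the next is at least 72 h away | Enter zero, wait for next scheduled time | No, inside the window |

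**Length of the window.** Late window = (days to next dose × 24 h) − 72 h.
- Days 1, 8, 29, 36, 57 and 64 are followed by a 7-day gap: 7 × 24 − 72 = 168 − 72 = 96 h (4 days).
- Days 15, 43 and 71 are followed by a 14-day gap: 14 × 24 − 72 = 336 − 72 = 264 h (11 days).

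So 6 + 3 = 9 of 9 ixazomib doses have a window in which the texts differ. In the last 72 hours before the next dose they agree, because 7.4 then also gives no late dose.

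**Example.** A patient forgets the Day 8 capsule.
- Remembered on Day 10: Day 15 is 5 × 24 = 120 h away, which is at least 72, so 7.4 permits the dose. The diary says wait until Day 15.
- Remembered on Day 13: Day 15 is 2 × 24 = 48 h away, so 7.4 does not permit the dose and both texts lead to waiting.

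**Size per event.** A full cycle at the starting dose is 9 × 4 = 36 mg. One dose handled differently is 4/36 = 1/9 = 11.1% of that cycle's ixazomib. At the reduced levels in Section 8.1 the fraction for a cycle at one dose level is still 1/9.

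**Effect on the design figures.** None. The operating characteristics in Section 16.22 depend only on patient numbers, cut-offs and success rates. An exact binomial calculation gives 0.0954 at a true rate of 30% and 0.8526 at 50%, matching the printed 0.095 and 0.853.

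**The case against.** The strongest reply is that the two texts can both be obeyed. Section 7.4 grants an option and does not oblige anyone to take a late dose. The diary contains no prohibition. A patient who waits has not breached 7.4. This is correct, and it limits the point: these are not two mandatory rules that exclude each other. It does not remove the conflict, because the diary's plain direction is to wait and it never tells the patient that the option exists.

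A second reply is that staff will explain the rule. Section 7.4 expects patients to be instructed, Section 15.13 calls for full dosing instructions for take-home ixazomib, and Section 7.2 brings patients back at least every 21 days. A reader might infer that the diary is the only text patients hold. The documents do not support that: other instructions are required, and the consent pages were not available for review. Still, nothing in the protocol says that the diary's missed-dose sentence is to be overridden.

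A third reply is that the record can cope with late doses. This also stands. The diary has an ixazomib box for each day, so a Day 8 dose taken on Day 10 would appear as a zero on Day 8 and 4 mg on Day 10. The fault lies in the instruction, not in the layout for recording a late dose.

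**Conclusion.** The inconsistency is real and confined to ixazomib. It can arise after any of the nine doses in a cycle, for 96 hours after six of them and 264 hours after three. Each time it changes what is taken, the difference is one dose: 1 of 9, or 4 of 36 mg at the starting dose. This assumes that 7.4's missed-dose sentence refers to ixazomib, as its placement indicates, and that the patient remembers inside the window and would have taken the capsule.

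Three stronger readings are tempting and should not be drawn.
- **Average loss of exposure.** If one assumed 1 to 2 forgotten doses per patient in Cycle 1, the texts could differ by up to 1/9 to 2/9, or 11% to 22%, of that cycle's ixazomib. The documents give no forgetting rate and zero is possible, so this describes a hypothetical affected patient and not the cohort.
- **Loss of evaluability.** Section 13.8 reserves a major violation for severe departures in Cycle 1 that put evaluability for the primary endpoint in question. Nothing shows that one forgotten dose would reach that level.
- **Damage to the primary analysis.** Sections 16.12 and 16.311 make eligible, consented patients evaluable once treatment has begun, apart from major violations, with no threshold of delivered dose. No analysis in Section 16 uses diary data.

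The point is worth correcting because it concerns what patients are told to take of a self-administered study drug and the correction is cheap.

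**What to change.** Reconcile Section 7.4 and Appendix II so that the missed-dose instruction for ixazomib is the same in both. Which rule stands is for the clinical team to decide; this review takes no position on it. If the rules for ixazomib and dexamethasone then still differ, give each drug its own missed-dose sentence in the diary; if they end up the same, one sentence is enough. It would also help to name ixazomib in the missed-dose sentence of 7.4.

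No extra date field is needed, because the diary already provides a box for each day. The cost is a wording amendment to the diary and, depending on the decision, to 7.4. Sample size, decision rules and analyses do not change.
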